**Table 6-6. AMG 340 Dose Modification Guidelines for Adverse Events**

Grade	Interruption/ Delay	Specific Management	Re-start Guidance	Permanent Discontinuation
Gastrointestinal events related to AMG 340 (continued)				
≥ 3	Interruption/delay until event has improved to grade ≤ 1	Gastrointestinal (GI) toxicities should be managed according to the local standard of care and institutional guidelines	
 
Re-start possible if successfully managed and improvement to ≤ grade 1 in ≤ 14 days.
 
Delay of next infusion: 
 
≤ 7 days: Administer the delayed infusion (as long as the next scheduled infusion is > 6 days from delayed infusion) and follow the schedule of assessments for the cycle day on which the infusion was originally planned.
 
> 7 days: Skip the delayed infusion and resume schedule of assessments for the next scheduled infusion
 
 
 
Hospitalization: 48 hours
 
Dose modification: Resume at the same dose or reduce to next lower dose if clinically indicated
 
	If subject missed more than 2 consecutive doses of AMG 340 OR In case of reappearance of same event at grade 4 OR In case of repeat grade ≥ 3 event despite dose reduction

Page 12 of 19

Abbreviations and footnotes defined on last page of table.

**Table 6-6. AMG 340 Dose Modification Guidelines for Adverse Events**

Grade	Interruption/Delay	Specific Management	Re-start Guidance	Permanent Discontinuation
Any other AMG 340-related events not meeting DLT criteria				
≥ 3	Interruption/delay required if deemed intolerable and/or clinically significant by the subject or investigator and not responding to appropriate medical management until event has improved to grade ≤ 1	N/A	
 
Re-start possible if successfully managed and improvement to ≤ grade 1 in ≤ 14 days.
 
Delay of next infusion: 
 
≤ 7 days: Administer the delayed infusion (as long as the next scheduled infusion is > 6 days from delayed infusion) and follow the schedule of assessments for the cycle day on which the infusion was originally planned.
 
> 7 days: Skip the delayed infusion and resume schedule of assessments for the next scheduled infusion
 
 
 
Hospitalization: 48 hours
 
Dose modification: Resume at the same dose or reduce to next lower dose if clinically indicated
 
	If subject missed more than 2 consecutive doses of AMG 340 OR In case of reappearance of same event at grade 4 OR In case of repeat grade ≥ 3 event despite dose reduction

Page 13 of 19

Abbreviations and footnotes defined on last page of table.

**Table 6-6. AMG 340 Dose Modification Guidelines for Adverse Events**

Grade	Interruption/Delay	Specific Management	Re-start Guidance	Permanent Discontinuation
Any Non-AMG 340-related events				
4	Interruption/ delay required if deemed intolerable by the subject or investigator and not responding to appropriate medical management until event has improved to grade $\leq 1$	N/A	
 
Re-start possible if successfully managed and improvement to <math>\leq</math> grade 1 in <math>\leq 28</math> days.
 
Delay of next infusion: 
 
<math>\leq 7</math> days: Administer the delayed infusion (as long as the next scheduled infusion is <math>> 6</math> days from delayed infusion) and follow the schedule of assessments for the cycle day on which the infusion was originally planned.
 
<math>> 7</math> days: Skip the delayed infusion and resume schedule of assessments for the next scheduled infusion
 
 
 
Hospitalization: 48 hours
 
Dose modification: Resume at the same dose or reduce to next lower dose if clinically indicated
 
	If subject missed more than 2 consecutive doses of AMG 340 OR In case of reappearance of same event at grade 4

Page 14 of 19

Abbreviations and footnotes defined on last page of table.

**Table 6-6. AMG 340 Dose Modification Guidelines for Adverse Events**

Pituitary Gland Dysfunction (González-Rodríguez and Rodríguez-Abreu, 2016; Brahmer et al, 2018)

Monitor for signs and symptoms of pituitary gland dysfunction, TSH, FT4, cortisol, and ACTH throughout study (prolactin, FSH, LH, testosterone/estradiol only at baseline and EOT)

Abnormal hormone monitoring result or clinical suspicion of pituitary gland dysfunction (headache, fatigue, asthenia, impaired vision, vomiting, hypotension, amenorrhea, impotence)

Diagnostic tests: Consider brain MRI (if clinically indicated) with or without contrast with pituitary/sellar cuts in subjects with multiple endocrine abnormalities and/or with new headache or vision changes. Evaluate ACTH, AM Cortisol, TSH, FT4, electrolytes and consider evaluating LH, FSH, and testosterone levels in males or estrogen in females.

Obtain endocrinology consultation for hypophysitis or if clinically indicated

Once pituitary gland dysfunction is confirmed, hold further treatment with AMG 340 pending completion of evaluation. Manage pituitary dysfunction according to NCCN or ASCO guidelines for Management of Immune-Related Adverse Events in Patients Treated with Immune Checkpoint Inhibitor Therapy (NCCN Guidelines, 2022; Brahmer et al, 2018).

Once stabilized on any replacement hormones and taking 10 mg or less of prednisone or equivalent may consider restarting AMG 340. If subject experienced grade 3 or higher pituitary dysfunction, must discuss with medical monitor prior to restarting treatment.

Continue endocrinological surveillance

Hepatotoxicity
For Stopping and Rechallenge Rules please refer to Section 11.7 .

Page 15 of 19

Abbreviations and footnotes defined on last page of table.

Table 6-6. AMG 340 Dose Modification Guidelines for Adverse Events

CTCAE Grade e	Interruption/ Delay f	Specific Management	Re-start Guidance f	Permanent Discontinuation f
Monkeypox Infection				
Grade 1: Asymptomatic or mild symptoms; clinical or diagnostic observations only; intervention not indicated	Interruption is not required unless the subject must be isolated for the event per local standard of care and institutional guidelines taking into consideration the benefit/risk of withholding treatment	Follow local guidelines and standard of care for Monkeypox treatment and isolation, if applicable.	If interruption is required: 
 
• Resolution of Monkeypox infection
 
• Resume at the same dose
 
	None
Grade 2: Moderate symptoms: minimal, non-invasive intervention indicated; limited age-appropriate instrumental ADLg	Interruption required until the event resolves	Follow local guidelines and standard of care for Monkeypox treatment and isolation, if applicable.	 
 
• Resolution of Monkeypox infection
 
• Resume at the same dose
 
 	None

Page 16 of 19

Abbreviations and footnotes defined on last page of table.

**Table 6-6. AMG 340 Dose Modification Guidelines for Adverse Events**

CTCAE Grade e	Interruption/ Delay f	Specific Management	Re-start Guidance f	Permanent Discontinuation f
Monkeypox Infection				
Grade 3: Severe or medically significant but not immediately life-threatening; hospitalization or prolongation of existing hospitalization indicated; limited selfcare ADLh	Interruption required until the event resolves	Follow local guidelines and standard of care for Monkeypox treatment and isolation, if applicable.	

Resolution of Monkeypox infection

Resume at the same dose or lower dose as clinically indicated

	Permanently discontinue investigational product therapy, if a subject required treatment interruption greater than 28 days due to grade 3 infection considering the individual benefit/risk
Grade 4: Life-threatening; consequences; urgent intervention indicated	Interruption required until the event resolves	Follow local guidelines and standard of care for Monkeypox treatment and isolation, if applicable.	

Resolution of Monkeypox infection

Reduce to next lower dose

	Permanently discontinue investigational product therapy, if a subject required treatment interruption greater than 28 days due to grade 4 Monkeypox infection considering the individual benefit/risk

Page 17 of 19

Abbreviations and footnotes defined on last page of table.

**Table 6-6. AMG 340 Dose Modification Guidelines for Adverse Events**

CTCAE Grade e	Interruption/Delay	Specific Management	Restart Guidance f	Permanent Discontinuation f
SARS-CoV-2 infection and COVID-19 disease				
Grade 1: Asymptomatic or mild symptoms; clinical or diagnostic observations only; intervention not indicated	Interruption required until at least 5 days i since positive SARS-CoV-2 test or since resolution of acute symptoms .	Follow local guidelines and standard of care for COVID-19 treatment and isolation	

Resolution of the acute symptoms

Subject tests negative for SARS-CoV-2,

If subject continues to test positive for SARS-CoV-2 more than 5 daysi after initial positive test or after resolution of symptoms, resume investigational product only after discussion with subject and reassessment of individual risk/benefit

Resume at the same dose

	None
Grade 2: Moderate symptoms: minimal, non-invasive intervention indicated; limited age-appropriate instrumental ADL	Interruption required until at least 5 days i since resolution of acute symptoms	Follow local guidelines and standard of care for COVID-19 treatment and isolation	

Resolution of the acute symptoms

Subject tests negative for SARS-CoV-2,

If subject continues to test positive for SARS-CoV-2 more than 5 daysi after resolution of symptoms, resume investigational product only after discussion with subject and reassessment of individual risk/benefit

Resume at the same dose

	None

Page 18 of 19

Abbreviations and footnotes defined on last page of table.

Table 6-6. AMG 340 Dose Modification Guidelines for Adverse Events

CTCAE Grade e	Interruption/Delay	Specific Management	Restart Guidance f	Permanent Discontinuation f
SARS-CoV-2 infection and COVID-19 disease				
Grade 3: Severe or medically significant but not immediately life-threatening; hospitalization or prolongation of existing hospitalization indicated; limited self- care ADL	Interruption required until at least 10 days since resolution of acute symptoms	Follow local guidelines and standard of care for COVID-19 treatment and isolation	
 
Resolution of the acute symptoms
 
Subject tests negative for SARS-CoV-2 
 
If subject continues to test positive for SARS-CoV-2 more than 10 days after resolution of symptoms, resume investigational product only after discussion with subject and reassessment of individual risk/benefit
 
 
 
Resume at the same dose or reduce to next lower dose if clinically indicated
 
	Permanently discontinue investigational product therapy if subject required treatment interruption greater than 28 days due to grade 3 COVID-19 infection
Grade 4: Life- threatening; consequences; urgent intervention indicated	Interruption required until at least 10 days since resolution of acute symptoms	Follow local guidelines and standard of care for COVID-19 treatment and isolation	
 
Resolution of the acute symptoms
 
Subject tests negative for SARS-CoV-2 
 
If subject continues to test positive for SARS-CoV-2 more than 10 days after resolution of symptoms, resume investigational product only after discussion with subject and reassessment of individual risk/benefit
 
 
 
Resume at the same dose or reduce to next lower dose if clinically indicated
 
	Permanently discontinue investigational product therapy if subject required treatment interruption greater than 28 days due to grade 4 COVID-19 infection

Page 19 of 19

ACTH = adrenocorticotrophic hormone; ASCO = American Society of Clinical Oncology; BiPAP = bilevel positive airway pressure; CRS = cytokine release syndrome; COVID-19 = coronavirus disease 2019; CPAP = continuous positive airway pressure; CT = computed tomography; **CTCAE = Common Terminology Criteria for Adverse Events**; DLT = dose-limiting toxicity; ECG = electrocardiogram; ECHO = echocardiogram; EOT = end of treatment; FSH = follicle stimulating hormone; FT4 = free t4; ICANS = immune effector cell associated neurologic syndrome; IL6 = interleukin6; IV = intravenous; IVF = intravenous fluid(s); LH = luteinizing hormone; MRI = magnetic resonance imaging; **N/A** = not applicable; NCCN = National Comprehensive Cancer Network; NSAIDs = non-steroidal anti-inflammatory drug(s); RTPCR = real-time polymerase chain reaction; SARS-CoV-2 = severe acute respiratory syndrome coronavirus 2; SOC = standard of care; TLS = tumor lysis syndrome; TSH = thyroid stimulating hormone

a American Society for Transplantation and Cellular Therapy (ASTCT) grading system for CRS (Lee et al, 2019).

b Fever is defined as temperature  $\geq 38^{\circ}\text{C}$  not attributable to any other cause. In subjects who have CRS then receive antipyretic or anticytokine therapy such as tocilizumab or steroids, fever is no longer required to grade subsequent CRS severity. In this case, CRS grading is driven by hypotension and/or hypoxia.

c CRS grade is determined by the more severe event: Hypotension or hypoxia not attributable to any other cause. For example, a subject with temperature of  $39.5^{\circ}\text{C}$ , hypotension requiring 1 vasopressor, and hypoxia requiring low-flow nasal cannula is classified as grade 3 CRS.

d Low-flow nasal cannula is defined as oxygen delivered at  $\leq 6 \text{ L/minute}$ . Low-flow also includes blow-by oxygen delivery, sometimes used in pediatrics. High-flow nasal cannula is defined as oxygen delivered at  $> 6 \text{ L/minute}$ .

e Document severity of COVID-19 or Monkeypox related adverse events utilizing the “Infection and Infestations – Other, specify” category per CTCAE version 5.0 as specified in the clinical protocol.

f Amgen Medical Monitor to decide based on investigational product safety risk and patient population whether to allow a subject who demonstrates a clinical benefit with a documented response of stable disease or better to resume therapy if there are reasons that the above dose withholding and restarting rules cannot be implemented. The investigator should contact and discuss these reasons with Amgen Medical Monitor. The investigator must obtain written agreement from Amgen Medical Monitor before any changes in the dose modification rules can be implemented.

g Instrumental Activities of Daily Living (ADL) refer to preparing meals, shopping for groceries or clothes, using the telephone, managing money, etc.

h Selfcare ADL refer to bathing, dressing, and undressing, feeding self, using the toilet, taking medications, and not bedridden.

i Amgen Medical Monitor to decide if investigational product should be interrupted for 10 days for grade 1 or grade 2 COVID-19 adverse event, based on investigational product safety risk and patient population.

#### **6.2.2.4 Infusion Interruptions/Delays/Withholding and Re-start in Case of Technical/Logistical Issues**

Events leading to infusion interruption or delay for technical/logistical reasons may include: technical problem with the infusion pump or the investigational product is incorrectly prepared or administered.

##### **Infusion Interruptions due to Technical/Logistical Issues**

The IV infusion administration of AMG 340 should not be interrupted, if possible. In case of infusion interruption, due to any technical or logistic reason, the interruption should be as short as possible, and the infusion continued at the earliest time possible.

In case of infusion interruption of  $\leq$  2 hours, the IV infusion administration can be restarted. In case of infusion interruption of  $>$  2 hours, immediately consult with Amgen Medical Monitor to determine if:

- investigational product stability is sufficient to administer the remaining infusion or
- a new infusion can be administered or
- the dose should be withheld

For short-term (120 minutes) infusions, if the remaining infusion can be administered, no specific precautions have to be taken. If a new infusion can be administered, follow the procedures in the Schedule of Activities (Section 1.3) or the cycle day on which the original (interrupted) infusion was administered. Premedication as described in Section 6.1.5 for treatment cycle 1 should be administered.

Any interruption of an infusion should be recorded in the eCRF, providing the start and stop date/time of the infusion if the interruption is  $>$  2 hours.

##### **Infusion Delay due to Technical/Logistical Issues**

If the infusion delay was  $\leq$  7 days, the dose can be administered without specific precautions. Procedures performed will follow the schedule of assessments for the cycle day on which the infusion was originally planned. The following infusion should then be administered after 21 ( $\pm$  1) days (eg, if the day 8 infusion needs to be delayed for logistical issues, and could only be administered on day 10, the next infusion should be administered 21 days later [ $\pm$  1 day]). The  $\pm$  1-day window is allowed until the original dosing schedule is met again.

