#### **6.1.5 Other Protocol-required Therapies**

All other protocol-required therapies including, dexamethasone, diphenhydramine, acetaminophen, ranitidine, tocilizumab (or siltuximab if tocilizumab is not available), that are commercially available are not provided or reimbursed by Amgen (except if required by local regulation). The investigator will be responsible for obtaining supplies of these protocol-required therapies.

Subjects will be premedicated twice with dexamethasone. Subjects will be premedicated with dexamethasone (10 mg PO or IV) or equivalent 12 to 16 hours prior to AMG 340 administration, and then again with dexamethasone 10 mg IV or equivalent within 1 hour of AMG 340 administration. If a subject does not experience an infusion-related reaction (IRR) or an immune-mediated toxicity (IMT; eg, CRS or NT) in a given cycle, the dexamethasone premedication dose may be reduced to 5 mg IV. If a subject does not experience an IRR or IMT in a cycle where they received 5 mg dexamethasone IV as premedication, dexamethasone may subsequently be omitted from the premedication regimen. If a subject experiences an IRR or IMT at any time, or if the subject undergoes an intra-subject dose escalation, they should be premedicated with 10 mg dexamethasone with the next dose of AMG 340 and tapered as described above.

Subjects will also routinely be premedicated with diphenhydramine (25 to 50 mg IV) or equivalent (eg, cetirizine 10 mg orally [PO] x 1), acetaminophen 650 to 1000 mg PO,

and ranitidine 150 mg PO/IV or equivalent, 15 to 60 minutes prior to AMG 340 infusion to reduce the risk and severity of hypersensitivity reactions commonly observed with mAb therapy. Subjects may also be premedicated with tocilizumab (8 mg/kg IV) at the discretion of the investigator and after approval by the Medical Monitors.

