#### **6.2.2 Dosage Adjustments, Delays, Rules for Withholding or Restarting, Permanent Discontinuation**

##### **6.2.2.1 Amgen Investigational Product: AMG 340**

The reason for dose change of AMG 340 is to be recorded on each subject's CRF(s).

Subjects experiencing CRS must continue to be hospitalized as described in [Table 6-6](#) and as deemed appropriate by the investigator. Subjects should be monitored for CRS symptoms, including vital signs and pulse oximetry at least every 2 hours for 12 hours, or until CRS grade  $\leq 1$ , whichever is earlier.

Re-starting treatment after an interruption/delay due to an adverse event or if the interruption/ delay was  $> 72$  hours, regardless of the reason, should be performed under medical supervision. Dexamethasone premedication is mandatory prior to re start, and prior to re-escalation to the target dose in case of dose reduction. The following assessments should be performed as per the Schedule of Activities for cycle 1, depending on duration of hospitalization:

- vital signs, pulse oximetry
- physical examination
- neurological examination (only in case the treatment interruption was due to a neurologic event)
- weight
- ECOG
- safety labs (hematology, chemistry, coagulation, urinalysis)

The subject should be hospitalized for up to 48 hours after re-start of the infusion depending on the specific adverse event that has led to the interruption/delay (causality and severity, see [Table 6-6](#) for adverse event management and restart guidance) or tolerability prior to delay for logistical reason and as per agreement with the Amgen Medical Monitor. **Re-introduction of the step dosing may be required for long delays and should be considered on a case-by-case basis with the Amgen Medical Monitor.**

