### **6.5 Treatment Compliance**

When subjects are dosed at the site, they will receive AMG 340 directly from the investigator or designee, under medical supervision. The date and time of each dose administered in the clinic will be recorded in the source documents and recorded in the CRF.

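### For logistical dose delays over 72 hours and up to 7 days, Protocol 6.2.2.1 makes dexamethasone mandatory at restart while 6.2.2.4 asks for no added precautions

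*Protocol*

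**What the plan says.** **Section 6.2.2.1** sets the restart rule. It applies after any interruption or delay caused by an adverse event. It also says that restart after an interruption or delay of more than 72 "hours, regardless of the reason, should be performed under medical supervision. Dexamethasone premedication is mandatory prior to re start". The section then lists assessments to be done on the cycle 1 schedule, depending on how long the subject is hospitalized. It allows a stay of up to 48 hours that depends on the adverse event concerned "or tolerability prior to delay for logistical reason and as per agreement with the Amgen Medical Monitor".

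**Section 6.2.2.4**, in the paragraph on infusion delay for technical or logistical reasons, says that if the delay was at most 7 "days, the dose can be administered without specific precautions". Procedures follow the originally planned cycle day. The illustration given is "if the day 8 infusion needs to be delayed for logistical issues, and could only be administered on day 10".

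**Section 6.1.5** sets routine premedication: dexamethasone 10 mg given 12 to 16 hours before AMG 340, and 10 mg again within the hour before it. After a cycle without an infusion-related reaction (IRR) or immune-mediated toxicity (IMT), the dose may be reduced to 5 mg IV. After a further clean cycle at 5 mg, "dexamethasone may subsequently be omitted from the premedication regimen". Dexamethasone is reinstated for anyone who "experiences an IRR or IMT at any time, or if the subject undergoes an intra-subject dose escalation, they should be premedicated with 10 mg".

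**The concern.** A premedication that one section calls mandatory is, on an ordinary reading, a specific precaution that another section says is not needed. The 6.2.2.4 delay paragraph has no exception at 72 hours and does not refer to 6.2.2.1. Section 6.1.5 does not close the gap, because a dose delay is not among its triggers for going back to 10 mg.

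Cytokine release syndrome is the identified risk of AMG 340 (Section 2.3.1), and dexamethasone is part of the routine premedication. After the same logistical delay, one site could give dexamethasone and another none, each able to point to protocol text. What is at stake is consistent safety handling at restart, not any statistical result.

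**Working it through.** No stated figure has to be reproduced. The check compares the texts and adds simple arithmetic on the time windows and the taper.

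**1. Overlap of the two rules.** The 6.2.2.1 trigger is a delay over 72 h. The 6.2.2.4 limit is 7 days × 24 = 168 h. The overlap is 168 − 72 = 96 h, or 4 days.

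| Logistical delay | 6.2.2.1 | 6.2.2.4, delay paragraph |
|---|---|---|
| up to 72 h | not triggered | no added precautions |
| over 72 h, up to 168 h | dexamethasone mandatory | no added precautions |
| over 168 h | dexamethasone mandatory | silent |

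**2. Does 6.2.2.1 reach logistical delays?** Yes. Its trigger is independent of cause, and its hospitalization sentence names logistical delay. It cannot be read as a rule for adverse events only.

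**3. The protocol's own example.** Day 10 − day 8 = 2 days = 48 h, which is under 72 h. The example lies outside the overlap and does not settle it.

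**4. Whose dexamethasone differs?** Take the fastest taper under 6.1.5, with no IRR or IMT:
- cycle 1: 10 + 10 = 20 mg
- cycle 2: 5 mg
- cycle 3: 0 mg

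Cycle 3 day 1 is 2 × 21 + 1 = study day 43. Before then the subject is still on routine dexamethasone and the conflict has little practical effect.

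**5. Size of the difference.** Section 6.2.2.1 states no dose. The candidates in 6.1.5 are 5 mg (last taper step), 10 mg (reinstatement dose) and 20 mg (full regimen). Which one is meant is an assumption.
- Dexamethasone already omitted: 5 − 0 = 5 mg to 20 − 0 = 20 mg.
- On 5 mg: 5 − 5 = 0 mg to 20 − 5 = 15 mg. There is a difference only if 6.2.2.1 means more than the current dose.

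The 5 mg cycle assumes a single dose. Section 6.1.5 does not say whether the dose given 12 to 16 hours ahead is dropped, halved or kept. A reduced cycle could therefore total 5, 5 + 5 = 10, or 10 + 5 = 15 mg. The gap to the full regimen would then be 15, 10 or 5 mg, so 0 to 15 mg is the outer range.

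**6. What falls outside the conflict.**
- If an infusion had started and a new one replaces it, the interruption paragraph of 6.2.2.4 already says: "Premedication as described in Section 6.1.5 for treatment cycle 1 should be administered". The delay paragraph has no such sentence.
- Medical supervision adds nothing, because Section 6.5 says of subjects dosed at the site that "they will receive AMG 340 directly from the investigator or designee, under medical supervision".
- The extra assessments and the hospital stay in 6.2.2.1 are conditional, so they do not clash as firmly as the dexamethasone rule.

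**The case against.** The strongest reply is that these are not opposite instructions. Section 6.2.2.4 is permissive, 6.2.2.1 is mandatory, and giving dexamethasone complies with both. Silence about premedication in the delay paragraph need not switch off an unqualified rule elsewhere, and the waived precautions might not include a standing premedication at all. The 0 mg comes from 6.1.5, where omission is optional, so sites may already differ among these subjects without any delay. The affected subjects have tolerated earlier doses. Finally, the overlap could equally be removed by narrowing 6.2.2.1, and the documents do not show which rule the sponsor intended.

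Much of this limits the weight of the point. Dual compliance is possible, the group is narrow, and the milligram range is an assumption that adds no evidence for the inconsistency. But the text still allows a site to follow one section and miss a step that another calls mandatory. The interruption paragraph of 6.2.2.4 spells out premedication and the delay paragraph does not, so a reader may fairly conclude that nothing is added. Variation that 6.1.5 permits in undelayed dosing does not excuse ambiguity where 6.2.2.1 removes the choice.

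**Conclusion.** The inconsistency is real and minor. Two rules apply to logistical delays over 72 and up to 168 hours, with no stated order of precedence. The firm consequence is limited to subjects in cycle 3 or later whose dexamethasone has been omitted and whose delay arose before any infusion started. They would receive 0 mg if the site relied on 6.2.2.4 and the 6.1.5 taper, against a mandatory dose taken here as 5 to 20 mg. The documents do not allow an estimate of how many subjects this would affect. No DLT count, endpoint, sample size or error rate depends on it.

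**What to change.** - In 6.2.2.4, restrict the waiver to logistical delays of 72 hours or less, and refer longer ones to the restart conditions in 6.2.2.1, including mandatory dexamethasone. The 48-hour example remains valid.
- In 6.2.2.1, state which 6.1.5 dexamethasone dose applies at restart.
- As a separate cross-reference correction, have Section 11.10, which sends readers to 6.2.2.4 for general restart guidance, cite 6.2.2.1 as well.

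The stricter reading is preferred because it applies a safeguard the protocol already calls mandatory. If the sponsor does intend to waive dexamethasone for logistical delays of 3 to 7 days, 6.2.2.1 should say so explicitly.

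The cost is one changed threshold, one added dose and two cross-references at the next amendment. For a few delayed subjects it means an extra dexamethasone dose and a few added checks.
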